## Protocol

### Abstract

**Objective:** Adolescents and young adults (AYA) living with chronic illnesses often struggle to adhere to daily oral medication regimens. Mobile health (mHealth) interventions are a promising avenue to support AYA in improving adherence, such as through delivering human coaching following the Supportive Accountability Model via mobile devices. AYA have reported increased use of and preference for text message communication over phone calls, so more investigation is needed to understand how cell phone support could be efficaciously delivered.

**Methods:** A randomized, controlled, 3-arm pilot trial will evaluate the impact of Cell Phone Support (CPS) on medication adherence. Conditions will be CPS delivered by phone calls (CPS-C), CPS delivered by text messages (CPS-T), or automated text message reminders (ATR). Participants will include AYA with various chronic illnesses (i.e., solid organ transplant, epilepsy, type 2 diabetes, sickle cell disease), aged 15-20 years ( $N = 60$ ). Randomization will be done via stratified blocks based on sex assigned at birth and focal diagnosis. Outcomes will include intervention engagement, participant satisfaction, and medication adherence, assessed using multi-method measurement. Additionally, focus groups will be used to assess the impact of CPS and understand how patients and healthcare providers experience the intervention.

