## **Design**

After passing eligibility screening and completing pre-treatment questionnaires, participants will be randomly assigned (1:1:1) to one of three 12-week groups: CPS delivered through voice-based phone calls (CPS-C), CPS delivered through text messaging (CPS-T), or automated text message reminders (Automated Reminders). A research colleague outside of the team used rand( ) function in Excel to create randomization blocks of 6 by sex assigned at birth and focal diagnosis. I hope to prevent substantial confounding by using stratified block randomization. For example, among the first 6 female participants with organ transplants, 2 would be assigned to CPS-C, 2 would be assigned to CPS-T, and 2 would be assigned to ATR.

The research colleague placed cards in sealed envelopes indicating the group assignment, and after the participant signed the consent form, the PI opened the envelope and informed the participant of the group they had been assigned to.

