## **Analytic Plan**

We will begin by examining the distribution and missingness of our outcome of interest, VAS. To take advantage of every available data point and account for repeated measures clustered within individual participants, we will run mixed-effect models in {STATA/SAS/R}, using a nested model-building process. If VAS is normally-distributed, we will specify linear mixed-effects models; otherwise, we may need to transform or dichotomize the outcome to ensure model assumptions are met. We will first run a simple model with only time (0, 6, 12, 18 weeks) as a Level I fixed effect predictor and VAS as a dependent variable, with the participant identification number included as a Level II random effect due to intra-individual correlation of VAS over time. Then, we will run increasingly complex models with intervention assignment (Cell Phone Support calls or texts n = 40 versus automated text reminders n = 20) included as a Level II fixed effect predictor, and then sex assigned at birth, focal medical diagnosis, medication complexity, age, and racial/ethnic identity as Level II fixed effect predictors, as well, to adjust for known or theoretical covariates. I will examine the impact of including increasing number of hypothesized predictors on model fit by examining AIC and  $R^2$ , and pare down the model if the model fit does not improve with all the hypothesized predictors included. This will lead to presenting parsimonious models that estimate the independent effect of the intervention on outcomes of interest, adjusted for all other predictors in the models. Finally, I will also assess whether model assumptions were met by plotting residuals versus fitted values. When I am

confident I have developed the most parsimonious, best-fitting model, I will calculate effect size estimates for the average difference in mean VAS between the Cell Phone Support call and text groups ( $n = 40$ ) and the automated text reminder group ( $n = 20$ ).

Then, we will follow the sample approach to predicting MEMS Caps adherence outcomes, and depression, social support, and self-efficacy. We will also run exploratory analyses using electronic-health record abstracted values (e.g., immunosuppressant levels, anti-epileptic drug levels, hemoglobin A1C, mean corpuscular volume/fetal hemoglobin) within focal diagnosis groups.

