Finally, for exploratory purposes, we will calculate pre-post effect sizes for subgroups of interest to explore whether interventions are comparably efficacious by focal diagnosis, gender, and racial/ethnic identity. Stratification was used to reduce the variation in potential confounders to be spread similarly between conditions, but that is not always entirely successful, especially in a small pilot trial. Therefore, we will conduct exploratory analyses including measured covariates as potential confounders or effect modifiers in the model-building process.

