Cell Phone Support to Promote Medication Adherence Among Adolescents and Young Adults With Chronic Illness

NCT04241627

8/8/2022

This randomized pilot trial tested three different digital health interventions against one another (CPS-C, n = 11, CPS-T, n = 12, and ATR, n = 11). We are interested in the impact on self-reported medication adherence. We have 6 different measures of dependent variables (VAS1w, VAS2w, VAS3w, VAS1m, VAS2m, VAS3m). We assessed our dependent variables 4 occasions, at 0 weeks (pre-tx), 6 weeks (mid-tx), 12 weeks (post-tx), and 18 weeks (follow-up). We would like to run mixed-effect models to test for intervention effects of 1) both CPS conditions (CPS-C and CPS-T, n = 23) versus ATR (n = 11); and 2) the CPS conditions against each other, ignoring ATR (CPS-C, n = 11 versus CPS-T, n = 12). I also have covariates (sex assigned at birth, diagnosis, age) that we can include during nested model building procedures, and include in final reported models if they lead to best fit.

Can we begin by examining the distributions of our dependent variables, and discuss whether we should use linear mixed-effects models; otherwise, we may need to transform or dichotomize the outcome or use a different type of model (poisson? Negative binomial?) to ensure model assumptions are met?

Then, can we evaluate the impact of missing data on my results by re-running these analyses using inverse probably weighting. It is possible that missing data will not be completely at random (i.e., participants with lower medication adherence may also be less likely to adhere to the online survey schedule).

Finally, I would like to calculate effect sizes for subgroups (see the final table). See tables on the next pages.

Blank Tables

Table 5

Best-Fitting Models Predicting Self-Reported Adherence for Both CPS Conditions (C and T) versus ATR (N = 34)

Dependent Variables	VAS1w			VAS2w			VAS3w			VAS1m			VAS2m			VAS3m		
	Estimates	CI	p															
Fixed Effects																		
Intercept																		
Time																		
Intervention Group (both CPS versus ATR)																		
Random Effects																		
σ^2																		
τ_{00}																		
τ_{11}																		
ρ_{01}																		
ICC																		
N																		
Observations																		
Marginal R ² / Conditional R ²																		
AIC																		

Note—Make ATR the reference group so the estimate tells us how the combined CPS groups compare

Table 6

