Best-Fitting Models Predicting Self-Reported Adherence for CPS-T versus CPS-C (N = 23)

Dependent Variables	VAS1w			VAS2w			VAS3w			VAS1m			VAS2m			VAS3m		
	Estimates	CI	p															
Fixed Effects																		
Intercept																		
Time																		
Intervention Group (CPS-T versus CPS-C)																		
Random Effects																		
σ^2																		
τ_{00}																		
τ_{11}																		
ρ_{01}																		
ICC																		
N																		
Observations																		
Marginal R ² / Conditional R ²																		
AIC																		

Note—Make CPS-C the reference group so the estimate tells us how CPS-T compares

Table 7

Exploratory Analyses Estimating Effect Sizes Using Self-Reported Outcomes Past Week (Pre-Post... Baseline to 12 weeks)

Subgroup	n	d	CI	p	Subgroup	n	d	CI	p
VAS1w									
Total Sample	--	--	--	--	Young Men	--	--	--	--
CPS Combined vs. ATR	34				CPS Combined vs. ATR				
CPS-T vs. CPS-C					CPS-T vs. CPS-C				
Sickle Cell Disease	--	--	--	--	Young Women	--	--	--	--
CPS Combined vs. ATR	14				CPS Combined vs. ATR				
CPS-T vs. CPS-C					CPS-T vs. CPS-C				
Solid Organ Transplant	--	--	--	--	Latinx	--	--	--	--
CPS Combined vs. ATR	10				CPS Combined vs. ATR				
CPS-T vs. CPS-C					CPS-T vs. CPS-C				
Type 2 Diabetes	--	--	--	--	Black	--	--	--	--
CPS Combined vs. ATR	10				CPS Combined vs. ATR				
CPS-T vs. CPS-C					CPS-T vs. CPS-C				
VAS2w									
Total Sample (N = 34)	--	--	--	--	Young Men	--	--	--	--
CPS Combined vs. ATR					CPS Combined vs. ATR				
CPS-T vs. CPS-C					CPS-T vs. CPS-C				
Sickle Cell Disease (n = 14)	--	--	--	--	Young Women	--	--	--	--
CPS Combined vs. ATR					CPS Combined vs. ATR				
CPS-T vs. CPS-C					CPS-T vs. CPS-C				
Solid Organ Transplant (n = 10)	--	--	--	--	Latinx	--	--	--	--
CPS Combined vs. ATR					CPS Combined vs. ATR				
CPS-T vs. CPS-C					CPS-T vs. CPS-C				
Type 2 Diabetes (n = 10)	--	--	--	--	Black	--	--	--	--
CPS Combined vs. ATR					CPS Combined vs. ATR				
CPS-T vs. CPS-C					CPS-T vs. CPS-C				
VAS3w									
Total Sample (N = 34)	--	--	--	--	Young Men	--	--	--	--
CPS Combined vs. ATR					CPS Combined vs. ATR				
CPS-T vs. CPS-C					CPS-T vs. CPS-C				
Sickle Cell Disease (n = 14)	--	--	--	--	Young Women	--	--	--	--
CPS Combined vs. ATR					CPS Combined vs. ATR				
CPS-T vs. CPS-C					CPS-T vs. CPS-C				

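### Choosing sex, focal diagnosis and age by model fit makes the reported tests slightly anti-conservative; one covariate set should be fixed in advance, with both stratifiers always in

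*SAP*

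**What the plan says.** The protocol's Abstract states: "Randomization will be done via stratified blocks based on sex assigned at birth and focal diagnosis". The Design section says that a colleague outside the team used Excel to "create randomization blocks of 6 by sex assigned at birth and focal diagnosis".

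The SAP's opening request lists "covariates (sex assigned at birth, diagnosis, age) that we can include during nested model building procedures", and would "include in final reported models if they lead to best fit". The protocol's Analytic Plan has the same rule for a longer list, which adds medication complexity and racial/ethnic identity. It examines AIC and R-squared and would "pare down the model if the model fit does not improve with all the hypothesized predictors included".

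On balance, the Analytic Plan says "Stratification was used to reduce the variation in potential confounders to be spread similarly between conditions", concedes that this may fail in a small pilot, and answers with "exploratory analyses including measured covariates as potential confounders or effect modifiers in the model-building process".

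No section requires sex and diagnosis to stay in the final model. Tables 5 and 6 of the SAP are titled as best-fitting models. Each has six outcome columns, one AIC per column, and fixed-effect rows for intercept, time and intervention group only. Neither document states an order of entry, an alpha level or a degrees-of-freedom method.

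**The concern.** An analysis should normally reflect the factors that restricted the randomisation. Here the stratifiers stay in only if the same data show a better fit, and the interval and p-value are then computed as if the chosen model had been fixed beforehand. That understates uncertainty, and more so in small samples. If selection is run separately for each outcome, which the one-AIC-per-column layout suggests but does not state, the six columns could also carry different covariates.

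The stake is modest. The protocol's Power Analysis says the pilot is to supply effect sizes for future proposals, so those estimates and their intervals should come from one known model.

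**Working it through.** **The plan's own figure.** The documents give no type I error for the selection rule. The nearest figure is the power of about 87% at d = 0.85. With 40 against 20 participants and a two-sided 5% level:

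z = 0.85 / √(1/40 + 1/20) − 1.96 = 0.85 / 0.2739 − 1.96 = 1.14, giving power of 87.4%.

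The stated figure is reproduced, which supports 5% as the working level.

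**Inputs from the documents.** The SAP gives arms of 11, 12 and 11; contrasts of 23 v 11 (N=34) and 12 v 11 (N=23); and diagnosis groups of 14, 10 and 10. The protocol gives blocks of 6 within sex by diagnosis.

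**Assumptions.** Sex is split 50/50. Strata explain 0, 15 or 30% of between-person variance, shared equally by sex and diagnosis. Age has no effect. Data are complete and there are no random slopes.

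**Method.** The analysis is at person level. On balanced four-visit data the participant-mean analysis gave the same likelihood differences and t values as a random-intercept model, to about four decimals. For each candidate model, AIC = n·ln(RSS/n) + 2p. In the model with the smallest AIC, the group estimate divided by its model SE is referred to t on n − p degrees of freedom.

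**Type I error (%) at strata share 0/15/30%**

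| Rule | N=34 | N=23 |
|---|---|---|
| Chain: none, +sex, +diagnosis, +age | 5.6 / 5.5 / 5.3 | 6.1 / 5.8 / 5.7 |
| All three covariates or none | 5.4 / 5.2 / 4.9 | 5.8 / 5.4 / 5.2 |
| Chain over sex and diagnosis only | 5.7 / 5.1 / 5.0 | 5.9 / 5.5 / 5.2 |
| Sex and diagnosis kept, age selected | 5.4 / 5.2 / 5.3 | 5.8 / 5.7 / 5.5 |
| Sex and diagnosis kept, no selection | 5.1 / 5.0 / 4.8 | 5.0 / 4.9 / 4.9 |

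Rows 3 and 4 use 20,000 null trials (Monte Carlo SE about 0.16 points). The others use 50,000 (SE 0.1).

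Repeat simulations, some with other stratum effects or all-subsets selection, widen the ranges slightly. Selecting only the stratifiers gives 4.9-5.7% (N=34) and 5.1-6.0% (N=23). Selecting only age gives 5.1-5.4% and 5.4-5.8%. A fully fixed stratified model gives 4.8-5.3%.

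**Standard errors.** Under the first rule, the ratio of model SE to true SD is 0.977/0.976/0.986 (N=34) and 0.958/0.965/0.969 (N=23), so SEs are about 1-2% and 3-4% too small.

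**Sensitivity.**
- With a Wald z reference, even the fixed stratified model runs at about 5.8-6.8%.
- With the protocol's five-covariate list (race/ethnicity as one term, 8,000 trials), all-subsets selection with t inference gives about 5.9-8.2%.
- With random slopes and 20% of follow-ups missing (3,000 trials, SE 0.4 points, no Kenward-Roger correction), the chain gives 6.6/5.8/6.4% against 5.9/5.3/5.8% with strata kept at N=34. At N=23, run only with no stratum effect, it gives 7.1% against 6.0%.

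**The case against.** The strongest reply is that this hardly matters. The trial is a pilot with no stated alpha. Tables 5 and 6 hold 6 × 2 = 12 unadjusted group p-values. If outcomes correlate 0.5-0.9 and the two contrasts are independent (both assumed), the chance of at least one false positive is already 20-37%, so half a point per test changes no conclusion. That stands, and it is why the point is minor.

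Second, the Analytic Plan can be read as adding the covariates as a group and removing them if the full set does not help. On that reading the error at N=34 is essentially nominal. This also stands: the chain is one reading, and its order is assumed.

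Third, the plan does not ignore covariates. The Analytic Plan puts them in the main model-building as well as in exploratory analyses, and the SAP sends selected covariates to the final reported models. A reader might infer from the table shells that retained covariates would be hidden, but blank shells do not show that. What remains is that neither document fixes the set, and the shells as drawn have no place to show it.

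**Conclusion.** The point holds as a small miscalibration from choosing covariates by fit: about 5.3-5.6% at N=34 and 5.6-6.1% at N=23 for the SAP's list, under the nested chain, complete data and t inference. Stratum effects and the sex split are assumptions, because the documents do not give them.

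Two stronger readings are tempting and should not be drawn.

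- **That optional stratifiers cause the whole excess, and that keeping them removes it.** The SAP puts age under the same rule. Where the strata are prognostic, selecting age alone adds at least as much as selecting the stratifiers. A nominal 5% also needs a small-sample reference distribution. With random slopes, which the tables' variance rows allow for, and missing data, strata-kept models still ran at 5.3-6.0% without a Kenward-Roger correction.
- **That the plan also risks intervals that are too wide.** That follows from never adjusting, where type I error falls to 2.3-2.6% if strata explain 30%. No section proposes this. Under the nested chain, average model SEs were too small in every setting, and selection lost no power.

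**What to change.** Pre-specify one covariate set for all six outcomes and both contrasts. Sex and focal diagnosis enter every reported model as fixed effects; age is declared in or out beforehand; none is chosen by AIC. Fit by REML with Kenward-Roger or Satterthwaite degrees of freedom. Add the covariate rows to Tables 5 and 6, and show fit-selected models only as sensitivity analyses. The choice of VAS scale or outcome distribution is a separate matter and is not needed for this change.

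The cost is SAP wording, three rows in each table and no new data. The stratifiers use 3 degrees of freedom (1 for sex, 2 for the three diagnoses in the SAP), leaving 34 − 2 − 3 = 29 and 23 − 2 − 3 = 18. Fixing age in would use one more.

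Against no adjustment, power at d = 0.85 changes as follows:
- If strata explain nothing: 60.1% against 60.9% (N=34) and 48.0% against 49.9% (N=23), a loss of about 1 and 2 points.
- If strata explain 15%: 67.0% against 61.9% and 53.9% against 49.2%, a gain of about 5 points at both sizes.

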## **Methods:**

### **Setting and Sample**

This study took place at Children's Hospital Los Angeles (CHLA), a large, urban, quaternary care, free-standing children's hospital that services approximately 36,000 unique AYA patients and cares for nearly one-third of LA County's Title V beneficiaries. As a safety net hospital, CHLA serves the most vulnerable children in the community, many of whom are at

high risk for gaps in care and adverse outcomes as they transition to adulthood. Participants in this study including patients who met the following inclusion criteria: 1) 15-20 years old at enrollment, 2) a patient at CHLA, 3) taking at least one oral medication per day, 4) provider and patient agreement that medication adherence is currently <80%, 5) Access to a cell phone, and 6) ability to speak and understand English. Participants were excluded if they had a cognitive impairment that precluded them from engaging in the consent/assent process or study protocol. Participants with diagnoses of autism spectrum disorder or intellectual disability were eligible as long as they were able to describe the purpose of the study, risks and benefits of enrolling, and summarize the research procedures in their own words. Non-English speaking patients were excluded because interventions were only developed in English at this stage. In addition, health care providers were enrolled to participate in focus groups and interviews. For healthcare providers, inclusion criteria was: 1) Status as a healthcare provider at CHLA providing care to adolescent and young adult patients taking daily oral medication, and 2) working in a CHLA subspecialty clinics which had agreed to refer patients to this study.

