### ***Primary Outcomes: Adherence Dependent Variables***

**Self-Reported Adherence.** In this study, medication adherence over the past 3 months was measured by a 3-item visual analogue scale (VAS) developed by Walsh, Dalton, and Gazzard (1998). The VAS uses percentage scales that contains the percent (%) value from 0 to 100 in which each point on the scale suggests the percent of time of medication adherence within a specified duration of time: 0% would mean “none of the time” or “never”; 50% would mean half of the time; 100% would mean “all of the time” or “always”, and numbers in between would mean amounts between “never” and “always” (Walsh, Dalton, & Gazzard, 1998). For each time frame, three visual analogue scales are provided, assessing 1) the percentage of the time patients took their medicine, 2) the percentage of the time patients took all the doses for the day, and 3) the percentage of the time patients took their medicine according to the directions (Walsh, Dalton, & Gazzard, 1998). Administering self-report adherence surveys by computer may decrease social desirability bias (Stirratt et al., 2015).

**MEMS Caps Adherence.** Participants (and caregivers, in the case of minor participants) will be oriented to using MEMS caps for one of the medications they take daily of their focal diagnosis (i.e., immunosuppressant for transplant, antiepileptic drug for epilepsy, hydroxyurea for sickle cell disease, metformin for type 2 diabetes). Microelectronic circuitry records the dates and times the caps are opened. We will calculate the percentage of prescribed doses that appear to have been taken through week 6, 12 and 18. MEMS caps are considered the “gold standard” in

adherence research and show moderate validity with both patient populations (Gerson et al., 2004; Cramer et al., 1995).

**Electronic Health Record Adherence Indicators.** Many of the focal diagnoses have regular labs collected as part of usual clinical care. For example, medication trough levels are usually collected periodically for the purpose of therapeutic drug monitoring for AYA living with solid organ transplants (i.e., immunosuppressant medications) and epilepsy (i.e., anti-epileptic drugs.). For other diagnoses, regularly collected labs are considered partially indicative of adherence, such as the hemoglobin A1C test for type 2 diabetes and mean corpuscular volume/fetal hemoglobin for sickle cell disease.

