### **Power Analysis**

Using STATA SE Version 15 software, we estimated the statistical power achieved with our proposed sample, assuming the Cohen's  $d$  effect size of 0.85 between groups seen in our preliminary data, within-subject intra-class correlation of 0.5 for repeated measures. We used the

design effect for clustered data (3 post-baseline measures, intraclass correlation=0.5) to compute the effective sample size for each group. The table below shows estimated power to detect differences in CPS (combined) versus automated reminders, and for the comparison of CPS strategies (original vs live text) in the total sample and by medical condition. To be more conservative, we also provide the statistical power for the CPS comparisons with a smaller effect size of 0.75 and 0.50. We also computed power to detect simple pre/post (e.g., baseline-12 week) changes between groups. There is approximately 87% statistical power for group comparisons using the combined sample with the effect size of 0.85; power is reduced for subgroup comparisons and the smaller effect size. However, as this study is a pilot randomized trial, the sample is more than sufficient to estimate effect sizes and assess feasibility for use in future proposals. See Table 1 for details.

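### The fallbacks named for a non-normal 0–100% VAS are chosen after seeing the data, and either waste power (dichotomising) or ignore the 100% ceiling (Poisson, negative binomial)

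*SAP*

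**What the plan says.** The Protocol (Primary Outcomes: Adherence Dependent Variables) defines the scale: "The VAS uses percentage scales that contains the percent (%) value from 0 to 100", with 0 meaning never and 100 meaning always. Its Analytic Plan specifies linear mixed-effects models if the VAS is normal; "otherwise, we may need to transform or dichotomize the outcome to ensure model assumptions are met". It describes a participant random effect only. The end product is to be an effect size for the average difference in mean VAS between the combined CPS arms and ATR.

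The SAP asks to look at the distributions first and to discuss whether linear mixed models suit. Otherwise "we may need to transform or dichotomize the outcome or use a different type of model (poisson? Negative binomial" (both count models carry a question mark). It applies this to six VAS variables. Tables 5 and 6 have rows for slope variance and intercept–slope correlation, which implies a random Time slope. Tables 7 and 8 ask for d.

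Neither document gives a cut-point, a rule for choosing among the fallbacks, or a model for a bounded score. The only adherence threshold anywhere is the entry criterion in Setting and Sample: "provider and patient agreement that medication adherence is currently <80" per cent.

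**The concern.** The form of the main outcome would be settled after the data are seen, separately for up to six variables, from a list that suits the scale poorly.

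- **Dichotomising** discards most of a 101-point scale in 34 people, and the cut is unset. If the 80% entry limit were used, most participants would be non-responders at week 0 by selection, so baseline would carry little information. Any other cut would be picked after the distribution had been examined.
- **Poisson and negative binomial** describe counts with no upper limit and can predict above 100%. Poisson also fixes the conditional variance at the mean: at a mean of 65 the SD would be √65 ≈ 8 points. Their natural result is a rate ratio, not the mean difference or d that the plan wants to carry forward.
- **Transforming** is named in both documents. It too moves the estimate off the percentage-point scale.

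At stake are power, the interpretability of the effect size for the next trial, and, for one version of the Poisson model, a misleading Time test.

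**Working it through.** **Inputs from the documents.** Effect sizes: "effect size of 0.85 between groups seen in our preliminary data", and also "with a smaller effect size of 0.75 and 0.50". Correlation: "within-subject intra-class correlation of 0.5 for repeated measures". Design-effect inputs: "3 post-baseline measures, intraclass correlation=0.5". Group sizes: 40 v 20 planned (Protocol, Analytic Plan); 23 v 11 and 11 v 12 actual (SAP).

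**Assumed, because the documents do not say.** Two-sided 5% level; VAS mean 50–75 and SD 15–30; the cut-points; no missing data.

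**1. The plan's own figure.** Power for means ≈ Φ(d·√[n₁n₂/(n₁+n₂)] − 1.96). For 40 v 20 and d = 0.85: √(800/60) = 3.651; 0.85 × 3.651 = 3.104; Φ(1.144) = 0.874. This matches the stated 87% as a plain comparison with one value per person. For 23 v 11: √(253/34) = 2.728; Φ(2.319 − 1.96) = 0.64.

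**2. Dichotomising, one visit.** For a normal score with control mean 60, SD 25 and a cut at 80, the control proportion is 1 − Φ(0.80) = 0.212. At d = 0.85 the CPS proportion is 1 − Φ(−0.05) = 0.520. The pooled-variance formula for two proportions at 23 v 11 gives about 39%, against 64% for means. Across several cuts:

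| Comparison | d | Means | Dichotomised | Loss (points) |
|---|---|---|---|---|
| 23 v 11 | 0.85 | 64% | 34–44% | 20–30 |
| 11 v 12 | 0.85 | 53% | 26–34% | 19–27 |
| 40 v 20 | 0.85 | 87% | 58–69% | 19–30 |
| 23 v 11 and 11 v 12 | 0.50 | 22–28% | 13–19% | 7–15 |

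A simulation with scores capped at 0 and 100 (23 v 11, SD 25, control means 50, 60 and 70, chi-square test, cut at 80 or the median, 1,500 runs per case) gives:

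- d = 0.85: losses from 60.9 − 46.7 = 14 to 63.3 − 33.5 = 30 points.
- d = 0.50: losses from 25.9 − 19.1 = 7 to 27.5 − 9.3 = 18 points.

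Beta-distributed scores with d about 0.92–0.96 and a cut at 80 lose about 15–29 points.

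**3. Dichotomising, three post-baseline visits.** The design effect for means is 1 + 2 × 0.5 = 2, so 23 v 11 counts as 34.5 v 16.5, with power 81% at d = 0.85. After the cut, the within-person correlation falls to about 0.31–0.32 and power to 61–69%. Over effect sizes 0.50–0.85 the loss is 7–22 points at the actual sizes and 5–22 at 40 v 20.

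**4. Poisson and the Time test.** With a random intercept only, the excess variance ratio is φ = SD²(1 − ICC)/mean, and a nominal 5% test rejects in about 2Φ(−1.96/√φ).

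- Mean 60, SD 15, ICC 0.5: φ = 112.5/60 = 1.88, rejection about 15%.
- Mean 60, SD 25, ICC 0.5: φ = 312.5/60 = 5.21, rejection about 39%.

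Simulation with no Time or group effect (34 people, 4 visits, capped and rounded scores, SD 15–25, ICC 0.5–0.7, 400 runs per case):

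| Model | Time test | Group test |
|---|---|---|
| Poisson, random intercept | 14–38% | 6.0–6.5% |
| Poisson, random intercept and slope | 6.5–7.2% | 6–8% |
| Negative binomial, random intercept | 2.5–4.5% | about 6% |
| Linear mixed model | 3.5–4.8% | 5.0–5.8% |

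Monte Carlo error is about 1 point near 5% and 2.5 points near 38%.

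**5. Possible replacements if residuals are skewed.** Under no effect at 23 v 11, a plain percentile bootstrap rejects in 6.6–8.4%, the t-test in 4.4–5.0% and a permutation test in 4.8–5.0%.

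**The case against.** The SAP wording is a request for discussion, with question marks after the count models, and the Protocol foresees AIC and residual plots that could expose a poor Poisson fit. That is fair. A reader might infer that a Poisson analysis has been adopted, and the documents do not say so. But this is the only SAP provided, and it leaves the form of the outcome open until the distributions have been seen.

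A reader might also infer that the fallbacks would produce false claims of an intervention effect. They do not support that. Tables 5 and 6 read the intervention from the group row, where rejection is 6–8% against 5–6% for the linear model. The marked inflation concerns Time, and only under Poisson with a random intercept and no overdispersion term. Tables 5 and 6 list a random slope, which nearly removes it. Because the Protocol describes only a participant random effect and allows models to be pared down by fit, the intercept-only version remains possible.

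It is also tempting to say that a dichotomy does not fit a capped scale, or that scores will pile up at 100. A dichotomy is a valid summary; its faults are lost power and the unset cut. The documents give no VAS distribution, and entry below 80% argues against heavy piling-up at week 0, though that entry judgement is not itself the VAS.

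**Conclusion.** The point stands as a recommended change. The scale is bounded, the fallbacks are chosen after the data are seen, and neither a cut nor a bounded model is specified.

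The cost of dichotomising is material but depends on assumptions:

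- roughly 14–30 points of power at one visit with d about 0.85–0.95 and 23 v 11;
- about 7–18 points at d about 0.50 at the actual sizes;
- about 5–22 points with repeated measures.

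No single figure should be quoted without these conditions, since the VAS spread and the cut are assumed. The count models are objectionable for the missing ceiling and the wrong scale. Inflation is a further objection to Poisson only, for Time only, and mainly without a random slope. The linear mixed model holds its level on the capped scores simulated here, so the fallbacks buy little.

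**What to change.** - Delete dichotomisation, Poisson and negative binomial as fallbacks for the main analysis, and state that a transformation will not replace the primary scale.
- State that each VAS score is analysed on 0–100 as a mean difference in percentage points from the linear mixed model.
- If residuals are skewed, keep that estimate and take the p-value and confidence interval from a re-randomisation test that respects the strata (sex assigned at birth and focal diagnosis), with the interval by inverting the test. Do not use a plain percentile bootstrap, which runs at about 7–8% type I error at 23 v 11.
- Report one bounded-scale model, fractional logit or an ordinal mixed model, as sensitivity only.
- Report any percentage at or above 80% at week 12 by arm descriptively.

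The cost is SAP wording and a few lines of code. The downside is a small loss of efficiency against a correctly specified bounded model.
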